### **Methodology**

The proposed study is a randomized trial of two methods of laboratory reporting in which physicians are the main research participants. At the time of positive urine culture results, the patient will be randomized by computer generated random number placed into serially numbered sealed, opaque envelopes in two equal groups. One group will receive restricted reporting, with a report that states "This POSITIVE urine culture may represent asymptomatic bacteriuria or urinary tract infection. If urinary tract infection is suspected clinically, please call the microbiology laboratory at [name] between 0900 to 2300, or the microbiology technologist on-call at [name] at night, for identification and susceptibility results." The other group will receive conventional reporting of identification and susceptibility. Physicians will then have the option of calling the laboratory to receive the results or not. Complete results will be released by telephone and Meditech to physicians who call to request them. Physicians will be informed about the study prior to initiation, and debriefed about the study after the results have been collected.

Inclusion criteria will include consecutive positive urine cultures collected from adults in acute care that are greater than or equal to 18 years of age. Inpatients must be admitted to Health Sciences Center or St. Clare's Mercy hospitals only, in order to facilitate access to inpatient records. Exclusion criteria will include pregnancy, antibiotic treatment at the time of collection, collection from an indwelling urinary catheter, patients in the Intensive Care Unit and patients with blood neutrophils  $<1.0$  within 7 days, which will help protect immunocompromised individuals. Furthermore, [name] will review patient charts at 24 and 72 hours and 7 days after collection to ensure patients experience minimal adverse events.

After randomization and reporting, a physician investigator will assess inpatients for the true diagnosis of AB or UTI. Health records will be accessed including demographics, treatment

decisions and outcomes (untreated UTI or pyelonephritis). Frequency of physician calls requesting complete reporting will be recorded.

The microbiology laboratory at Health Sciences Center receives 130 urine specimens per day, with 30 percent reported as significant growth (40 specimens per day). Twenty-five percent are submitted from inpatients. Method of collection will be determined prior to randomization. Study data collection and analysis will take place at the microbiology laboratory only.

The research hypothesis is that restricted reporting will reduce the rate of inappropriate treatment prescribed by physicians. Among inpatients, the expected rate of inappropriate treatment in the control group will be 45 percent, and 15 percent in the intervention group. Accepting a risk of type 1 error of five percent, and a risk of type 2 error of twenty percent, the study will recruit 84 patients. In order to account for missing data, recruitment will be increased to 100 patients. This will require approximately ten days of recruitment. The statistical test to be used is a comparison of proportions between two groups (T test, two sided analysis). Because true diagnosis may be biased by lack of access to clinical information, an intention to treat analysis including all patients randomized will be performed.

Physicians must remain unaware of the research project so that their treatment decisions are unbiased. However, a general notice will be sent to all physicians regarding the study design, and a debrief will be provided in which study results are presented and the option to withdraw data will be provided. This will cause physicians to feel less deceived while still not informing them of the study and thus will not change their behavior.

Physicians of discharged inpatients will be contacted at 7 days to assess for adverse events. Because recruitment will be brief, it is unlikely that physicians will have a second patient in the study.

Ethics permission will be sought from the local ethics board. Consent of patients or physicians will not be requested. In compliance with TCPS requirements, participants will experience no more than minimal risk. [name] who will assess inpatient charts at 24 and 72 hours and 7 days to surveil adverse events. If an adverse event occurs, the patient will be removed from the study immediately and given standard treatment. Physician consent will not be requested, as awareness of the study would bias treatment decisions.

The benefit of this study to patients includes a reduction in adverse events caused by inappropriate treatment. The risk to patients includes possible untreated UTI. The benefit to physicians includes education toward appropriate treatment of AB. The risk to physicians includes additional effort to access laboratory results for UTI.

Data collection will use a paper case report form, and entry into a password protected online database. Analysis will be performed using SPSS 20.0 (IBM). The only expense of the project will be the graduate student to collect the data, perform the analysis and write the manuscript. The manuscript will be published in a peer-reviewed journal and presented at a national conference.

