### **Research Objectives**

Research Question: Among inpatients with positive urine cultures reported by Health Sciences microbiology laboratory, would restricted reporting, as compared to standard reporting, lead to a reduction in the rate of inappropriate antibiotic therapy without an increase in UTI or pyelonephritis (kidney infection)?

Primary efficacy outcome: proportion of inappropriate antibiotic therapy prescribed by physicians based on published diagnostic criteria for AB and UTI [2, 4, 17] in an intention to treat population. Inappropriate therapy is defined as any treatment for AB, or no treatment for UTI, or treatment for UTI to which the isolated bacteria is resistant.

Primary safety outcome: proportion of untreated UTI and untreated bacteremia.

Secondary efficacy outcomes: proportion of calls from physicians requesting complete report, drug cost savings based on reduction in treatment.

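### Antibiotic use is checked at urine collection, but randomisation comes at the culture result; treatment begun in between is largely beyond the report's influence, yet is neither recorded nor allowed for in the analysis

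*Combined protocol and SAP*

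**What the plan says.** Under Methodology, the exclusions include "antibiotic treatment at the time of collection". Randomisation happens later: "At the time of positive urine culture results, the patient will be randomized". The one item that the section places before randomisation is how the specimen was taken: "Method of collection will be determined prior to randomization". Nothing addresses antibiotics begun between collection and result.

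Research Objectives defines the primary outcome: "Inappropriate therapy is defined as any treatment for AB, or no treatment for UTI, or treatment for UTI to which the isolated bacteria is resistant". The definition has no start date and no window tied to the report. The analysis set is everyone: "an intention to treat analysis including all patients randomized will be performed".

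The sample size assumes that "the expected rate of inappropriate treatment in the control group will be 45 percent, and 15 percent in the intervention group". It does not say whether these rates include treatment begun before the report.

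**The concern.** The hypothesis is about what the form of the report does to prescribing. A prescription written before the report exists cannot be prevented by it. By excluding patients already treated at collection, the plan partly accepts this, but the check is made at a time earlier than randomisation.

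For patients who start in between, the scoring is as follows:

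- **AB:** a failure in either arm. Because any treatment counts, this holds on a literal reading even if treatment is stopped after the report.
- **Urinary tract infection (UTI) treated with an active drug:** appropriate in either arm.
- **UTI treated with a drug to which the isolate is resistant:** a failure, if the early treatment is what is scored.

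In each case the outcome is largely fixed before allocation, and in expectation it is equally frequent in both arms. At stake are the power of a 100-patient trial and the ability to tell a report that does little from one that often arrives after the decision has been made.

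**Working it through.** **Inputs.** From Methodology: 45% v 15%, two-sided 5% type 1 error, 20% type 2 error, equal groups, 84 patients raised to 100 for missing data. Assumed, because the documents do not give it: f, the share of randomised patients who started antibiotics between collection and report. I use 5% and 10%, and take all of them to have AB.

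**The plan's own figure.** Without continuity correction, n per arm = [1.96√(2×0.30×0.70) + 0.8416√(0.45×0.55 + 0.15×0.85)]² / 0.30² = 35.4. With the correction, (35.4/4)×[1 + √(1 + 4/(35.4×0.30))]² = 41.8, so 42 per arm and 84 in total. The plan's 84 reproduces.

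**Power at 50 per arm.** For the uncorrected chi-square test, with p̄ the mean of the two rates:

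power = Φ{ [p₁−p₂ − 1.96√(2p̄(1−p̄)/50)] / √[(p₁(1−p₁)+p₂(1−p₂))/50] }

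Exact binomial enumeration gives the same whole percentages. With f = 0, power is 92%.

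*Case A: early-treated patients come on top of the planned rates.* The rates are f + (1−f)×0.45 and f + (1−f)×0.15, so the difference is 0.30×(1−f).

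*Case B: they lie within the 45% control rate, and the report cuts only the remainder by two thirds.* The rates are 0.45 and f + (0.45−f)/3.

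| Case | f | Control | Restricted | Difference | Power, unstratified | Power, stratified |
|---|---|---|---|---|---|---|
| A | 5% | 47.75% | 19.25% | 28.5 points | 87% | 91% |
| A | 10% | 50.5% | 23.5% | 27.0 points | 81% | 89% |
| B | 5% | 45% | 18.3% | 26.7 points | 83% | 88% |
| B | 10% | 45% | 21.7% | 23.3 points | 70% | 82% |

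**Stratified column.** This is the Mantel-Haenszel test stratified by antibiotic status at randomisation, from simulated trials in which the early-treated count in each arm is binomial. If everyone in the early-treated stratum is a failure, that stratum adds nothing to the observed-minus-expected count and nothing to its variance. The test then rests on the patients not yet treated.

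The pooled stratified difference stays essentially where it was. In case A at f = 10% it is about 0.90×0.30 + 0.10×0 = 0.27, the unstratified value. The gain is in precision only.

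*Case C: 45% and 15% already include early-treated patients.* The difference is still 30 points and unstratified power is still 92%, so nothing is lost against the plan. If every early-treated patient is a failure, f cannot exceed the 15% restricted-arm rate. Stratifying still helps: power is about 96% to 98% for f of 5% to 10%.

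**If some early-treated patients have UTI.** With f = 10% and half of them UTI treated actively, the rates on the case A model are 0.05 + 0.90×0.45 = 45.5% and 0.05 + 0.90×0.15 = 18.5%. The difference is again 27 points and power is 83.5%. The pilot figures in the Literature Review (2% UTI, 17.8% positive) suggest UTI in about 2/17.8 = 11% of positives, if both percentages are of all 415 specimens. AB would then be the usual case.

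**Sensitivity to the test.** With the continuity correction that reproduces 84, power at 50 per arm is 88% with f = 0. At f = 5% and 10% it is 81% and 74% in case A, and 76.5% and 62% in case B. All these figures use 100 complete patients, so missing data would lower them.

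**The case against.** The strongest reply is that the all-patient comparison is what Research Objectives asks for: whether a reporting policy lowers inappropriate therapy among inpatients with positive cultures, by intention to treat. If some treatment starts before the report, the policy really does have a smaller overall effect. This stands. A reader might infer that the estimate is biased; the documents do not support that. The smaller difference is a legitimate estimand, measured with avoidable noise.

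The size is also open. f appears nowhere in the documents, and on the case C reading there is no shortfall. Three of the four unstratified scenarios in the table still meet the planned 80% power on the uncorrected test. A reader might take f = 20%, where case B gives 41%, as evidence of a badly underpowered trial. Nothing in the documents supports that share, and under case C it is impossible if all early-treated patients are failures.

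A reader might also infer that all treatment begun before the report counts as failure. It does not: UTI treated early with an active drug is scored as appropriate. And if the sponsor means treatment started or continued after the report, stopping early treatment becomes something that the report can influence. The current wording does not say so.

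What survives is the timing gap, the open-ended outcome wording and the lack of any planned record of treatment start relative to the report. None of these depends on f.

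**Conclusion.** The concern holds as a cheap improvement to the design and analysis, not as a flaw that invalidates the trial. The plan admits patients whose outcome is largely settled before the intervention, and has no means of identifying them. Their effect is expected to be the same in both arms, so this does not by itself favour restricted reporting. Unless the planned rates already include them, it makes a useful report harder to detect.

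For an assumed f of 5% to 10%, all with AB, the cost at 50 per arm is 5 to 11 percentage points of power in case A (92% to 87% or 81%) and 9 to 22 points in case B (92% to 83% or 70%). In case C it is nil. Stratifying recovers much of the loss, but leaves the pooled difference as it is.

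**What to change.** 1. Before the envelope is opened, at the step where method of collection is already settled, record whether antibiotics have been started since collection.
2. Stratify the primary comparison by that status (Mantel-Haenszel test and stratified risk difference), keeping all randomised patients. Exclude no one on this ground after randomisation.
3. Pre-specify a further analysis of treatment in patients not on antibiotics at randomisation. The subgroup is defined before allocation, so the comparison stays randomised, and it isolates the decisions that the report can influence.
4. State in the outcome definition how treatment begun before the report is scored, including when it is later stopped, and whether 45% and 15% include such patients.

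The cost is one extra chart field, a few sentences of text and slightly more analysis. An optional alternative is to apply the existing antibiotic exclusion at randomisation. That also keeps intention to treat intact, but it narrows the population and slows recruitment.

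### No masking is stated for the AB/UTI diagnosis that largely decides the primary outcome and untreated UTI, and intention to treat cannot correct a wrong diagnosis

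*Combined protocol and SAP*

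**What the plan says.** All references are to the combined protocol and SAP.

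- **Primary efficacy outcome (Research Objectives):** "proportion of inappropriate antibiotic therapy prescribed by physicians based on published diagnostic criteria for AB and UTI". The definition follows: "Inappropriate therapy is defined as any treatment for AB, or no treatment for UTI", with a third component for UTI treated with a drug that the isolate resists.
- **Safety (Research Objectives):** "Primary safety outcome: proportion of untreated UTI and untreated bacteremia".
- **Who makes the diagnosis, and when (Methodology):** "After randomization and reporting, a physician investigator will assess inpatients for the true diagnosis of AB or UTI". The same paragraph gives access to health records, including treatment decisions, and adds: "Frequency of physician calls requesting complete reporting will be recorded".
- **Where the data are handled (Methodology):** "Study data collection and analysis will take place at the microbiology laboratory only".
- **Response to a doubtful diagnosis (Methodology):** "Because true diagnosis may be biased by lack of access to clinical information, an intention to treat analysis including all patients randomized" is to be carried out.
- **Missing data (Methodology):** recruitment rises from 84 to 100.
- **Safety review (Methodology):** charts are reviewed at 24 hours, 72 hours and 7 days.

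Three safeguards are stated: sealed opaque envelopes for allocation, treating physicians kept unaware of the project, and published diagnostic criteria. No statement covers masking of the person who assigns AB or UTI.

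**The concern.** The primary outcome combines two facts: what was prescribed and what the patient had. The first is a matter of record. The second is a judgement made after the report has gone out, by which time treatment may already have been decided. An assessor who knows the arm, or knows that antibiotics were given, may read borderline findings differently. The primary comparison would then partly reflect labelling rather than prescribing.

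The intention-to-treat sentence raises a second, separate problem. It names a classification difficulty (too little clinical information for a sound diagnosis) and answers it with a rule about the analysis set. A reader could believe that the difficulty has been dealt with when it has not.

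**Working it through.** **1. How far the label decides the outcome.** Apply the definition in Research Objectives to one patient under each label:

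| Prescribing | Labelled AB | Labelled UTI |
|---|---|---|
| Treated, isolate susceptible | inappropriate | appropriate |
| Treated, isolate resistant | inappropriate | inappropriate |
| Not treated | appropriate | inappropriate (also a safety event) |

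In two of three rows the label alone flips the result, hence *largely*. Untreated bacteremia does not depend on this label. The flips run in opposite directions: moving a treated patient from AB to UTI usually removes a failure, while moving an untreated patient creates one. The direction of any net bias therefore cannot be deduced.

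**2. Whether a stated safeguard covers the assessor.** Envelopes conceal the allocation until randomization, and the diagnosis comes later. The unawareness concerns treating physicians. Published criteria narrow discretion but do not hide arm or treatment.

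**3. The plan's own figure.** Inputs from Methodology: 45% and 15%, two-sided 5%, power 80%, equal groups. The difference is 0.30 and the mean rate 0.30.
- Uncorrected n per arm = [1.960·√(2·0.30·0.70) + 0.842·√(0.45·0.55 + 0.15·0.85)]² / 0.30² = 35.43.
- With continuity correction: (35.43/4)·[1 + √(1 + 4/(35.43·0.30))]² = 41.83, so 42 per arm and 84 in total.

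This matches the plan. The sample size is not in dispute.

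**4. Illustration of arm-dependent labelling.** The error rates are assumed; the documents give none. Method: exact binomial enumeration, 50 per arm (100 randomized, none missing), pooled two-proportion z test, two-sided 5%. The planned t test agrees within 0.3 percentage points.

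A fraction f of inappropriate cases in one arm is recoded as appropriate, so the 45% rate becomes 0.45·(1 − f):

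| f | Recoded rate | No true effect (other arm 45%): rejection rate | Planned effect, control arm recoded (restricted arm 15%): power |
|---|---|---|---|
| 0 | 45% | 5.6% | 92.2% |
| 10% | 40.5% | 8.0% | 83.2% |
| 20% | 36% | 15.6% | 69.0% |
| 30% | 31.5% | 28.8% | 50.7% |

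**5. Offsetting error.** Recode 20% of failures in both arms. The planned rates become 0.45·0.8 = 36% and 0.15·0.8 = 12%. By the normal approximation, power is 81% (92% with no error), against 69% when only the control arm is recoded. With no true effect, both arms move to 36% and no false difference arises.

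**6. What intention to treat leaves untouched.** Suppose a fraction m of labels is wrong equally in both arms, regardless of treatment, and ignore resistant isolates. The observed rate is p(1 − m) + (1 − p)m. For m = 10%:
- control: 0.45·0.9 + 0.55·0.1 = 46%;
- restricted: 0.15·0.9 + 0.85·0.1 = 22%.

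The difference falls from 30 to 24 points, and power at 50 per arm falls from 92% to 72% (normal approximation). Every randomized patient is still analysed in the assigned arm, so intention to treat is fully satisfied and the loss remains. Masking would not remove this loss either, which is why the two problems need separate answers.

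**The case against.** **The criteria are published, and the plan may simply be silent on a masking that was intended.** The first part has weight, because criteria reduce discretion. They do not remove it: the plan itself allows that the diagnosis may be biased. As to the second, the point here is only that masking is not stated.

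**A reader might infer that the assessor will know the arm, or that the graduate student is unmasked.** The documents do not establish either. Placing the data work in the laboratory, together with "The only expense of the project will be the graduate student to collect the data, perform the analysis and write the manuscript", makes exposure plausible. It does not show what the assessor or the student sees.

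**Masking could collide with the safety chart review.** This stands. If the same person does both, withholding antibiotic orders could hide an untreated UTI from the reviewer. The documents do not show whether the roles are separate, so any fix must exempt that review.

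**The intention-to-treat sentence may only say whom to analyse.** As such it is sound, since it prevents selective exclusion of patients with an uncertain diagnosis. Its wording nevertheless ties it to biased diagnosis.

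**The increase to 100 already provides for missing data.** It does so in number only. It does not say how a patient who cannot be classified is counted.

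**The illustration is one-sided.** This is fair. It assumes a net shift in one arm, and its mildest case leaves power at 83%, above the planned 80%. Step 5 shows how far offsetting error softens it.

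**Conclusion.** The point holds as a gap in the design. The label that largely decides the primary outcome, and wholly decides which untreated patients count as untreated UTI, is assigned after reporting with no stated masking. Intention to treat is not a remedy for mislabelling. Both should be corrected.

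The size is illustrative: under assumed one-way error of 10 to 30%, rejection rates are about 8 to 29% with no true effect, and power is 83 to 51% at the planned rates. These figures rest on assumed error rates, no offsetting and 50 complete patients per arm. No figure is given for safety, because the plan states no denominator for the proportion of untreated UTI. With few such events likely, a single label could matter.

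A reader might conclude that the trial is biased towards restricted reporting. The documents do not support that: they give no misclassification rate, and the table in step 1 shows that relabelling can work in either direction.

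**What to change.** **Methodology, paragraph on assessment after randomization.** State that the physician investigator:
- records the signs and symptoms named in the criteria on the case report form;
- applies the published criteria;
- locks the diagnosis before viewing report type, laboratory calls or antibiotic orders, with culture results shown in the same form for both arms.

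Treatment and resistance are linked and scored afterwards.

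**Safety review.** State that this applies to outcome classification only and does not limit what the chart review at 24 hours, 72 hours and 7 days may see. If one person does both, the diagnosis is locked before treatment data are viewed where possible, and cases where this was not possible are recorded.

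**Methodology, intention-to-treat sentence.** Replace with, for example: *All patients randomized will be analysed in the arm assigned. Diagnosis will be classified by the published criteria and locked before treatment and report type are viewed, where feasible. Patients with too little information to classify are kept, and a sensitivity analysis counts them first as AB and then as UTI.*

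**Cost.** Protocol and form wording, plus some extra abstraction on about 100 charts; the sample size does not change. Whether existing staff suffice depends on whether the assessor and the safety reviewer are the same person, which the documents do not show. Masking may be incomplete where notes reveal treatment or a call, and it does not supply missing clinical information.

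### Physicians may withdraw data at the same debrief that presents the results, with no deadline, data lock or handling rule, so outcome-related removal from the intention-to-treat set is possible

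*Combined protocol and SAP*

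**What the plan says.** The relevant statements are in the Methodology and Research Objectives sections of the combined protocol and SAP.

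- **Timing.** Physicians will be "debriefed about the study after the results have been collected". A later Methodology paragraph adds that "a debrief will be provided in which study results are presented and the option to withdraw data will be provided".
- **Who may withdraw.** The text does not name them outright. The sentence concerns physicians, and the trial is one in which "physicians are the main research participants".
- **What their data are.** The primary efficacy outcome is the "proportion of inappropriate antibiotic therapy prescribed by physicians".
- **Prior opportunity to opt out.** "Consent of patients or physicians will not be requested". The debrief is the only point at which the plan offers physicians a way out.
- **Analysis set.** The Methodology section promises that "an intention to treat analysis including all patients randomized will be performed".

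The plan gives no closing date for withdrawal, no data lock and no statement on whether withdrawn data leave the analysis. The increase from 84 to 100 patients is for missing data and does not mention withdrawal.

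**The concern.** The person who decides whether a data point stays is the person whose decision that data point judges, and the choice is offered on the occasion when results are shown. Withdrawal could therefore depend on the outcome, on the arm (physicians see which kind of report they received) or on the reaction to the overall finding.

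Three things are left open: which comes first within the debrief, whether physicians learn how their own cases were classified, and whether withdrawn data are deleted from the analysis. If they are deleted, the analysis no longer contains all randomized patients and a known result may be altered. Removal that is related to outcome and unequal between arms would bias the primary comparison, in a direction set by the arm that loses events. Even if nothing untoward happened, a reader could not tell whether the reported set was fixed before or after results were seen.

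**Working it through.** **Inputs from the plan (Methodology):** 45% v 15% inappropriate treatment, two-sided 5% type I error, 20% type II error, equal groups, 84 patients raised to 100, comparison of proportions by T test.

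**Inputs assumed:** every withdrawal count and rate below, deletion of withdrawn patients, and 50 analysed per arm before withdrawal.

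**1. The plan's own figure.** Per arm, n = [1.960·√(2·0.30·0.70) + 0.842·√(0.45·0.55 + 0.15·0.85)]² / 0.30² = 35.4. With the continuity correction, n′ = (n/4)·[1 + √(1 + 4/(0.30n))]² = 41.8, so 42 per arm and 84 in total. This matches, and 84/(1 − 0.16) = 100. The sample size is not at fault, but extra patients cannot correct selective removal.

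**2. A result near the planned effect.** For a/n v b/m, the pooled variance is s² = [a(n−a)/n + b(m−b)/m]/(n+m−2), and t = (a/n − b/m)/√[s²(1/n + 1/m)]. For 22/50 v 8/50, s² = (12.32 + 6.72)/98 = 0.194 and t = 0.28/0.088 = 3.18, so p = 0.002. Deleting k control-arm events gives:

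| k | Control | Restricted | Difference | T test p | Fisher p |
|---|---|---|---|---|---|
| 0 | 22/50 | 8/50 | 0.28 | 0.002 | 0.004 |
| 2 | 20/48 | 8/50 | 0.26 | 0.005 | 0.007 |
| 5 | 17/45 | 8/50 | 0.22 | 0.016 | 0.020 |
| 7 | 15/43 | 8/50 | 0.19 | 0.036 | 0.053 |
| 8 | 14/42 | 8/50 | 0.17 | 0.053 | 0.085 |

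**3. A result near the threshold.** Start from 22/50 v 13/50:

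| Events deleted | T test p | Fisher p |
|---|---|---|
| none | 0.060 | 0.093 |
| 1, restricted arm | 0.041 | 0.057 |
| 2, restricted arm | 0.027 | 0.034 |
| 1 in each arm | 0.055 | 0.087 |
| 2 in each arm | 0.0502 | 0.080 |

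**4. How often two withdrawals matter.** Over all possible results at a true 45% v 15%, deleting two control-arm events turns a significant T test non-significant in about 5% of trials. Deleting two restricted-arm events turns a non-significant one significant in about 4%. The second figure is not a false-positive rate, because the effect is real in those trials.

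**5. Withdrawal as a rate.** Suppose each event is withdrawn independently with probability w. An arm with true rate p then shows about p(1−w)/(1−pw). For example, with w = 0.2 in the control arm only, 0.45·0.8/(1 − 0.09) = 0.396, and the difference is 0.396 − 0.15 = 0.246. Exact enumeration with the T test gives:

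| w | Control only: difference | Control only: power | Both arms: power | No effect (30% v 30%), restricted only: type I error | No effect, both arms: type I error |
|---|---|---|---|---|---|
| 0 | 0.30 | 0.92 | 0.92 | 0.050 | 0.05 |
| 0.1 | 0.27 | 0.87 | 0.90 | 0.057 | 0.05 |
| 0.2 | 0.25 | 0.79 | 0.87 | 0.079 | 0.05 |
| 0.3 | 0.21 | 0.67 | 0.84 | 0.12 | 0.05 |

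The damaging ingredient is imbalance between arms. Outcome-related withdrawal at the same rate in both arms costs some power and leaves type I error alone.

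**The case against.** The strongest reply is that the text is silent rather than contradictory. Results exist by the time of the debrief, the only stated analysis rule covers all randomized patients, and nothing says a withdrawal triggers re-analysis. On that reading the option never touches the primary analysis.

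It can also be said that the obvious motive, discomfort at being judged inappropriate, applies in both arms, where the bias is towards no effect and power stays above the planned 80%. Nothing in the plan explains why only restricted-arm physicians would withdraw, which the inflated type I error requires. Overturning a result near the planned effect takes 7 or 8 of 22 control events (32% to 36%) and none from the other arm. Since the plan thinks a second patient per physician unlikely, that means about 7 or 8 separate physicians. Any p-value close to 0.05 is fragile to one or two patients from any cause, and the one-patient flip in the example occurs with the T test but not with Fisher. Finally, consent is waived, and a physician who has not seen the results makes a less informed choice about withdrawal.

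Much of this stands as a limit on size. The harm is conditional, and one-arm withdrawal is a possibility the plan leaves open, not a prediction. It does not remove the gap. If withdrawals leave the analysis unchanged, the plan should say so; if they change it, the set is altered after the result is known. The plan does not say which.

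**Conclusion.** The concern holds. The plan couples results and withdrawal in one debrief, offers the choice to those whose prescribing is the outcome, and has no deadline, lock or handling rule to reconcile this with its promise to analyse everyone randomized. That much rests on the text alone.

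The size of any bias cannot be established, because the documents give no withdrawal rate. If withdrawn patients are deleted, a handful of one-sided withdrawals would matter little for a result near 45% v 15%, but one or two could decide a result near the threshold. Sustained one-arm withdrawal of 10% to 30% of events would cut power from 0.92 to between 0.87 and 0.67 (control arm), or raise type I error from 0.05 to between 0.057 and 0.12 (restricted arm, no true effect, 30% in both arms). Balanced withdrawal is largely harmless. The point should be fixed because the remedy is cheap, not because bias has been shown.

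**What to change.** Keep both the debrief and the withdrawal option, but separate them in time:

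1. After the last 7-day follow-up, tell physicians about the study and open a dated withdrawal window, before disclosing any arm-level result or any classification of their own patients.
2. Close the window, lock the data, analyse, and only then present results.
3. State whether withdrawn patients leave the primary analysis, and how that fits with the intention-to-treat commitment.
4. Report withdrawals by arm, with best-case and worst-case bounds over all randomized patients. For example, if 5 of 22 control events are withdrawn, the observed 17/45 v 8/50 gives a difference of 0.22. Counting the five as non-events gives 17/50 − 8/50 = 0.18, and counting them as events gives 22/50 − 8/50 = 0.28.

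The cost is protocol and ethics wording and a slightly later presentation of results. Physicians would decide without having seen the results, which makes the choice less informed. The ethics board must accept that, and its view cannot be judged from the documents. If it does not, items 3 and 4 are still worth adopting alone: they do not prevent selective removal, but they make it visible and bound its effect.
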